#### Pharmacokinetic in UGT2B17 extensive metabolizer

The pharmacokinetic data showed considerable inter-individual variability. There was a less than proportional increase in exposure parameters Cmax,ss and AUCt,ss from 10 to 30 mg bid, but a more than dose proportional increase from 30 to 70 mg dose group. The 120 mg bid dose group showed less than dose proportional increase compared to the 70 mg bid DG. Following 150 mg bid dosing, the exposure was only comparable to 70 mg bid DG, that was interpreted to be caused by usage of a higher tablet strength (150 mg) with dissolution problems. Unexpected high accumulation ratios were observed for both Cmax and AUCt for the three highest DGs (see Table 1.2.1:3) with also a high inter-individual variability.

#### Pharmacokinetic in UGT2B17 poor metabolizer

The inter-individual variability was considerably lower in PMs as compared to EMs. Exposure to BI 1323495 at steady state was approximately ~3 to 5-fold higher based on Cmax,ss and AUCt,ss in PMs as compared to EMs. The accumulation ratios at 10 mg bid and 30 mg bid were comparable between both PMs and EMs at the same dose level. However, the exposure in the 30 mg bid DG in PMs was at single dose twice as high as for the 70 mg

Proprietary confidential information © 2021 Boehringer Ingelheim International GmbH or one or more of its affiliated companies

bid DG in EM, but still did not lead to such high accumulations as observed in the higher dose groups in the EMs suggesting that the UGT2B17 metabolism plays a role in the unexpected high accumulation behavior in EMs. The exposure of the 30 mg bid DG in PMs was comparable to the 70 mg bid DG in EMs.

In the seven completed dose groups, three subjects ( 1 subject of the 70 mg bid DG and 2 subjects of the 120 mg bid DG) exceeded the pre-defined exposure caps of  $AUC_{0-24}$  (11500 nM\*h). The exposure of subject [REDACTED] following 150mg dosing was not observed but a predicted  $AUC_{0-24}$  at steady state, as this [REDACTED] subject discontinued from the study on Day 6 following PI decision linked to an AE .

Preliminary PK results do not indicate an obvious effect of gender on the pharmacokinetics of BI 1323495.

No obvious effects of genotype (\*1/\*1 versus \*1/\*2 EMs) on the pharmacokinetics of BI 1323495 was observed in the completed dose groups.

For further details refer to the IB ([c21238478-05](#)).

### 1.2.2. Itraconazole

Absorption of itraconazole solution is fast with maximum plasma concentration being reached within approximately 2.0 h after oral administration in fasting condition.

Bioavailability of itraconazole liquid increases by 10-70% when given under fasting condition compared to administration together with food. Mean peak plasma concentrations were 738 ng/mL after a single dose of 200 mg itraconazole solution (fasting) and 2500 ng/mL after 15 days of daily treatment with 200 mg itraconazole solution (fasting).

Pharmacokinetics of itraconazole is non-linear. The half-life of itraconazole after multiple doses of 200 mg once daily with solution formulation was approximately 40 h.

In the liver, itraconazole is metabolized extensively to more than 30 metabolites ([R17-3743](#)). Its main metabolite, OH-itraconazole, accounts for about twice the concentration of plasma itraconazole at trough. It has been shown *in vitro* that CYP3A4 is mainly responsible for the formation of this metabolite ([R18-2644](#)). FDA, EMA, and PMDA classify itraconazole as strong index inhibitor of CYP3A ([R18-0241](#), [P15-06991](#), and [P15-06298](#)). However, not only itraconazole contributes to the *in vivo* inhibition of CYP3A observed after itraconazole administration but also three of its metabolites (OH-itraconazole, keto-itraconazole, and N desalkyl-itraconazole) ([R10-1102](#)).

For further details, please refer to the package insert for ITRIZOLE® Oral Solution 1% ([R20-1269](#)).

### 1.2.3. Residual Effect Period

The Residual Effect Period (REP, i.e., the period after the last dose with measurable drug levels and/or pharmacodynamic effects still likely to be present) of BI 1323495 is approximately 7 days.

When given together with itraconazole (Treatment T), it is expected that plasma exposure of BI 1323495 could be increased (albeit within the exposures explored in the clinical trial

Proprietary confidential information © 2021 Boehringer Ingelheim International GmbH or one or more of its affiliated companies

1405-0001), and the time of relevant plasma exposure could be prolonged. This might result in a prolonged period in which adverse effects could potentially occur.

For the use of itraconazole in Treatment T, the REP is defined as 9 days after last administration of itraconazole on Day 7 in Period 2.

### 1.3. RATIONALE FOR PERFORMING THE TRIAL

The UGT2B17 polymorphism is geographically unequally distributed, with differences likely driven by ethnicity. Within Asian populations, the \*2/\*2 genotype is predominant, with UGT2B17 extensive metabolizers (EMs; genotypes \*1/\*1 or \*1/\*2) comprising only approximately 15% of the general population ([R19-1805](#)). The three parts of this trial take into consideration the distribution of this pharmacogenetic polymorphism in the Asian population.

#### SRD part and MD part

The objective of this trial is to investigate the safety, tolerability, pharmacokinetics and pharmacodynamics of BI 1323495 in healthy male Japanese subjects. The chosen population of healthy male subjects receiving single rising oral doses and multiple oral doses are considered adequate to provide the basis for the clinical development program of BI 1323495 in Japan. Additionally, investigation of difference between PM and EM of UGT2B17 genotype will provide more insight to development of BI 1323495.

In 1405-0002, PK after multiple administrations were investigated in Caucasian UGT 2B17 EM and PM populations. This result indicated that PK characteristics after multiple drug administration were slightly different between UGT2B17 phenotype groups (e.g., the exposure in the 30 mg bid DG in PMs was at single dose twice as high as for the 70 mg bid DG in EM, but still did not lead to high accumulations as observed in the higher dose groups in the EMs, etc...), which might be caused by UGT2B17 metabolic capability (please see in detail in section 1.2.1). Since the UGT2B17 polymorphism is geographically unequally distributed (e.g., UGT2B17 PM is predominant in Asian population), the investigation of PK after multiple drug administrations in Japanese could provide comprehensive PK taking account into the racial PK difference, which is beneficial for clinical development program of BI 1323495 in Asian region.

In the airways affected by neutrophilic inflammation, NE is considered a major component of the pathophysiology of emphysema development in COPD and of tissue destruction and exacerbations in CF. In MD parts, the NE activity after zymosan stimulation of peripheral blood will be assessed as a pharmacodynamic outcome for the effects of BI 1323495 after multiple drug administrations in UGT 2B17 PM population, which provides comprehensive PK-PD relationship covering both UGT 2B17 genotype groups.

The dose range selected for this trial is expected to cover the potential therapeutic dose range(s) in the further clinical development program of BI 1323495 for both UGT2B17 PMs and EMs.

### Drug-drug interaction (DDI) part

Based on *in vitro* data in human hepatocytes, BI 1323495 is metabolized via glucuronidation by UGT2B7 and UGT2B17 and via various phase I biotransformations by CYP 3A4. The *in vitro* ratio of metabolism via glucuronidation to oxidation was in the range of 7:1 to 2:1. Additionally, BI 1323495 is an *in vitro* substrate of P-glycoprotein (P-gp) ([c21238478-05](#)).

Therefore, in this trial, the focus is on the DDI victim potential of BI 1323495 with regard to CYP3A4 and P-gp inhibition as this may lead to clinically relevant increases in exposures with potential impact on patient safety. The victim potential of BI 1323495 upon inhibition of CYP 3A4 / P-gp in UGT2B17 EM has already been assessed (trial 1405-0009), suggesting that a modest increase in exposure to BI 1323495 in gMean AUC0-∞ and Cmax of 1.69- fold and 1.37-fold, respectively, occurs when administered together with itraconazole. In addition, dedicated DDI assessment in a UGT2B17 PM population is required to evaluate the comprehensive victim potential of BI 1323495 by strong CYP3A4/P-gp inhibitor considering UGT2B17 genotypes, since UGT2B17 PM, when treated with a strong inhibitor of CYP 3A4 and P-gp, lack two main metabolic pathways and may experience a more pronounced effect of CYP 3A / P-gp inhibition on exposures to BI 1323495. This DDI assessment in UGT2B17 poor metabolizers is performed in a Japanese population as the high prevalence of UGT2B17 PM subjects in this population greatly facilitates the conduct of this assessment.

Itraconazole is chosen for this trial as perpetrator drug, as this drug is recommended as strong inhibitor of CYP3A by EMA ([P15-06991](#)), as strong index inhibitor of CYP3A by FDA ([R18-0241](#)), and as strong inhibitor of CYP3A by PMDA ([P15-06298](#)) and it is an inhibitor of P-gp (R18-0241). Moreover, safety and tolerability of itraconazole were acceptable in previous drug-drug interaction trials ([c02336088](#), [c03355329](#), [c08928447](#)).

## 1.4. BENEFIT - RISK ASSESSMENT

Participation in this clinical trial is without any (therapeutic) benefit for healthy subjects. Their participation in the trial, however, is of major importance for the development of a new orally available drug, which is expected to improve the prognosis of patients with COPD and emphysema by slowing the natural course of the disease, especially the progressive decline in lung function and lung density associated with the progression of tissue destruction. Furthermore, it is expected that patients with CF will benefit by experiencing less frequent pulmonary exacerbations and slowing of the natural course of the disease.

### 1.4.1. Procedure-related risks

The use of an indwelling venous catheter or venepuncture for e.g. blood sampling may result in mild bruising, and in rare cases, in transient inflammation of the wall of the vein, or nerve injury, potentially resulting in paraesthesia, reduced sensibility, and/or pain for an indefinite period, as well as in feeling of light-headedness or in syncope.

The total volume of blood withdrawn per subject during the entire trial will not exceed the volume of a normal blood donation (400 mL). No health-related risk to healthy subjects is expected from withdrawal of this volume of blood.

#### 1.4.2. Drug-related risks and safety measures

##### Drug-induced liver injury

Although rare, a potential for drug-induced liver injury (DILI) is under constant surveillance by sponsors. Therefore, this trial requires timely detection, evaluation, and follow-up of laboratory alterations in selected liver laboratory parameters to ensure subjects' safety; see also Section [5.2.6.1.4](#), adverse events of special interest.

##### BI 1323495

BI 1323495 is a potent and highly selective inhibitor of NE. Taking into account the mode of action, the nature of the target, non-clinical findings, and the relevance of animal species and models, BI 1323495 is not considered a high-risk compound. Two compounds with the same mode of action as BI 1323495 have already been tested in phase I and II clinical trials with no relevant safety issues detected ([c21238478-05](#)).

The formation of active NE, together with two other neutrophil serine proteases (NSPs: Cathepsin G, Proteinase 3), is catalysed by Cathepsin C (CatC) in maturing neutrophil precursor cells in the bone marrow. A human genetic disease exists, Papillon-Lefèvre syndrome (PLS), in which patients completely lack functional NSPs (including NE) due to complete deficiency for CatC. The neutrophils of PLS patients upon activation are unable to release active NSPs, including NE. The phenotype of these patients can be looked at as a human model of a pharmacologically induced complete suppression of NE (and other NSPs). Despite this complete lack of functional neutrophil serine proteases, which may be expected to weaken the microbicidal capacity of neutrophils, the associated immunodeficiency in Papillon-Lefèvre syndrome patients is generally mild.

The target organs in the preclinical assessment of toxicity with BI 1323495 were the liver and kidney, and coagulation pathway in rodents, and as responsive organ, the immune system and coagulation pathway in the cynomolgus monkey.

Effects on the liver were indicated by increases in liver enzymes (Aspartate transaminase [AST], ALT, or GLDH), decreases in cholesterol and triglycerides, and an increase in total bilirubin in rats at 600 or 900 mg/kg/day. Biliary hyperplasia was observed in female rats given 900 mg/kg/day for 4-weeks. The liver findings were still present at the end of the 4-wk recovery period, but they were not seen in the 13-week toxicity trials although male rats achieved high exposures. The drug exposure was much higher in these animals than those expected in man and observed in the SRD trial 1405-0001.

*Risk mitigation and monitoring:* Although alterations are not specifically expected, liver function tests including total and direct bilirubin will be monitored as part of the standard safety laboratory assessments (see Section [5.2.3](#)). Subjects with impaired liver function will be excluded from participation in this trial.

Effects on the kidneys at exposures with BI 1323495 high above those expected in man were accompanied by increases in creatinine levels and changes in blood urea values in the 2-week mice and rat trials. In the 4-week trial in rats, tubular basophilia was observed in the

Proprietary confidential information © 2021 Boehringer Ingelheim International GmbH or one or more of its affiliated companies

kidneys of males and female rats at the highest dose tested. These effects were still present at the end of the 4-week recovery period. In the 13-week trial, tubular degeneration was seen in male rats at the highest dose tested but recovered fully within the 8-week recovery period.

*Risk mitigation and monitoring:* Serum creatinine, urea, and electrolyte levels will be assessed, and glomerular filtration rate will be estimated as part of the standard safety laboratory assessments (see Section 5.2.3). Subjects with impaired renal function will be excluded from participation in this trial.

The coagulation pathway was affected in rats, showing a dose-independent increase in fibrinogen. An increase is regarded toxicologically not relevant. A reduction in platelet counts was associated with BI 1323495 exposure in both rodent and non-rodent species. This was accompanied at very high exposures by minor increases in prothrombin time in male rats. No bleeding events occurred.

*Risk mitigation and monitoring:* Platelet count, prothrombin time and activated partial thromboplastin time (aPTT) will be measured as part of the standard safety laboratory assessments (see Section [5.2.3](#)). Monitoring will be done for any signs of bleeding or bleeding-related adverse events. Use of concomitant drugs that inhibit platelet aggregation or coagulation (e.g. acetylsalicylic acid) will be prohibited (ref. Section [4.2.2](#)).

The immune system showed an increase in the number of primarily B-lymphocytes in the cynomolgus monkey. In the spleen, increased cellularity in the lymphocyte-rich region was observed, and the lymph nodes showed an increase in germinal center development in the 13-week monkey trial at high exposures. These effects were considered to be toxicologically not relevant.

In the SRD and food effect trial, single dose administration of BI 1323495 up to 600 mg under fasted conditions and 100 mg under fasted and fed conditions was well tolerated, with no clinically relevant changes in safety lab, ECG, and vital signs observed (ref. Section [1.2.1](#)).

As with all drugs, the potential for hypersensitivity and allergic reactions has to be taken into consideration when BI 1323495 is administered.

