#### **5.2.3. Safety laboratory parameters**

For the assessment of laboratory parameters, blood and urine samples will be collected by the trial site at the time points indicated in the [Flow Chart](#) after the subjects have fasted for at least 10 h, except 4 h post dosing on Day 1 of SRD part and screening. For retests, at the discretion of the investigator or designee, overnight fasting is not required. The parameters that will be determined are listed in Tables [5.2.3: 1](#) and [5.2.3: 2](#). Reference ranges will be provided in the ISF, Section [10](#).

Manual differential white blood cell count or urine sediment examinations will only be performed if there is an abnormality in the automatic blood cell count or in the urinalysis, respectively.

Table 5.2.3: 1 Routine laboratory tests

Functional lab group	BI test name [comment/abbreviation]	A 	B 	C 	D 
Haematology	Haematocrit	X	X	--	X
	Haemoglobin	X	X	--	X
	Red Blood Cell Count/Erythrocytes	X	X	--	X
	White Blood Cells/Leucocytes	X	X	--	X
	Platelet Count/Thrombocytes (quant)	X	X	--	X
Automatic WBC relative	Neutrophils/Leukocytes; Eosinophils/Leukocytes; Basophils/ Leukocytes; Monocytes/Leukocytes; Lymphocytes/Leukocytes	X	X	--	X
Automatic WBC differential	Neutrophil, absol.; Eosinophils, absol.; Basophils, absol.; Monocytes, absol.; Lymphocytes, absol.	X	X	--	X
Manual differential WBC (if automatic differential WBC is abnormal and clinically relevant in the opinion of the investigator)	Neut. Poly (segs; Neutrophils Bands; Eosinophils/Leukocytes; Basophils/ Leukocytes; Monocytes/ Leukocytes; Lymphocytes/Leukocytes;				
Coagulation	Activated Partial Thromboplastin Time	X	--	--	--
	Prothrombin time	X	--	--	--
	INR (International Normalization Ratio)	X	--	--	--
	Fibrinogen	X	X	--	--
Enzymes	AST [Aspartate transaminase] /GOT	X	X	X	--
	ALT [Alanine transaminase] /GPT	X	X	X	--
	Alkaline Phosphatase	X	X	X	--
	Gamma-Glutamyl Transferase	X	X	X	--
	Creatine Kinase [CK]	X	X	--	--
	Creatine Kinase Isoenzyme MB [only if CK is elevated and clinically relevant in the opinion of the investigator]	X	X	--	--
Hormones	Thyroid Stimulating Hormone	X	--	--	--
Substrates	Glucose (Plasma)	X	X	--	--
	Creatinine	X	X	--	--
	GFR/ CKD-EPI	X	X	--	--
	Bilirubin, Total	X	X	--	--
	Bilirubin, Direct	X	X	--	--
	Protein, Total	X	X	--	--
	C-Reactive Protein (Quant)	X	X	--	--
	Cholesterol, total	X	--	--	--
Electrolytes	Triglyceride	X	--	--	--
	Sodium	X	X	--	--
	Potassium	X	X	--	--

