 A: parameters to be determined at Visit 1 and EOT

B: parameters to be determined at Visit 2 and 3 (for trial days and time points refer to [Flow Chart](#))

C: parameters to be determined at Visit 3 (for trial days and time points refer to Flow Chart)

D: parameters to be determined at Visit 2 (only for MD part)

 Microscopic examination if erythrocytes, leukocytes, nitrite or protein in urinalysis are abnormal in urine

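### Protocol 1.4.2 commits to measuring serum urea for the kidney signal, but Table 5.2.3: 1 has no urea row, so no urea measurement is scheduled

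*Protocol*

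**What the plan says.** Section 1.4.2, under BI 1323495, lists the kidney among the target organs in rodents. It reports that the kidney effects were "accompanied by increases in creatinine levels and changes in blood urea values in the 2-week mice and rat trials", and adds tubular findings in the 4-week and 13-week rat trials. It places these effects at exposures far above those anticipated in humans. The risk-mitigation paragraph that follows says: "Serum creatinine, urea, and electrolyte levels will be assessed, and glomerular filtration rate will be estimated as part of the standard safety laboratory assessments". It refers the reader to Section 5.2.3 and adds that subjects with impaired renal function are excluded.

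Section 5.2.3 makes its tables the working list: "The parameters that will be determined are listed in Tables" 5.2.3: 1 and 5.2.3: 2. Table 5.2.3: 1 assigns each test to sets A to D. The footnotes give the use of the two sets that matter here: "A: parameters to be determined at Visit 1 and EOT" and "B: parameters to be determined at Visit 2 and 3".

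SAP 7.8.2 describes the laboratory analysis in general terms and has no parameter list of its own.

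**The concern.** The site and the laboratory work from the table, not from the benefit-risk narrative. If urea has no row, a site that follows the protocol exactly will not order it, and a measurement presented as risk mitigation will not be made.

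Urea and creatinine are the two blood markers that Section 1.4.2 ties to the kidney findings. Estimated GFR adds little that is independent of creatinine, because creatinine is the only serum filtration marker in the table from which it could be computed. Without urea, the trial report could not say from scheduled data whether the second marker changed, including after 11 days of dosing in the MD part.

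**Working it through.** The plan gives no figure to reproduce. The check sets the commitments in Section 1.4.2 against the rows of Table 5.2.3: 1.

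| Analyte named under risk mitigation in 1.4.2 | Row in Table 5.2.3: 1 | Sets |
|---|---|---|
| Total and direct bilirubin (liver) | yes | A, B |
| Serum creatinine (kidney) | yes | A, B |
| Electrolytes (kidney) | yes, sodium and potassium | A, B |
| Estimated GFR (kidney) | yes, GFR/CKD-EPI | A, B |
| **Urea (kidney)** | **none** | **none** |
| Platelet count (coagulation) | yes | A, B, D |
| Prothrombin time, aPTT (coagulation) | yes | A |

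**Other places where urea could appear**

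- Substrates rows: glucose, creatinine, GFR/CKD-EPI, total and direct bilirubin, total protein, C-reactive protein, total cholesterol and triglyceride.
- Set C: AST, ALT, alkaline phosphatase and GGT only.
- Set D: haematology and white cell counts only.
- Urinalysis rows: stix items, with sediment only if certain stix results are abnormal.
- Table 5.2.3: 2: drug screen, infectious serology and chest x-ray.
- Flow charts, their footnotes and the SAP: no mention of urea or BUN. The only two mentions in either document are those in Section 1.4.2.

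So 3 of the 4 renal items are scheduled, and urea is in 0 of 4 sets.

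**Where urea would fall if it followed creatinine (every set A or B time point in the flow charts)**

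- SRD: screening and EOT (A); Day -1, 4 h, 24 h and 168 h (B). 2 + 4 = 6 per subject.
- MD: screening and EOT (A); Days -1, 2, 5, 8, 11 and 13 (B). 2 + 6 = 8 per subject.
- DDI: screening and EOT (A); Period 1 Day -1, 24 h and 71 h (B); Period 2 Day -3, 23 h and 167 h (B). 2 + 3 + 3 = 8 per subject.

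With the planned 36, 24 and 14 subjects, that is 36 × 6 + 24 × 8 + 14 × 8 = 216 + 192 + 112 = 520 scheduled occasions on which creatinine is measured and urea is not. The 74 planned subjects include 3 × 2 + 3 × 1 + 2 × 3 = 15 on placebo, so 74 − 15 = 59 would receive BI 1323495.

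**The case against.** **The table may be damaged.** Its group labels have slipped near the page end (the electrolytes label sits beside triglyceride), and the urinalysis block lists nine tests against eight marks per set. A lost urea row therefore cannot be ruled out. This caveat stands. It does not overturn the finding, because the Substrates rows run on without a visible gap and every other analyte named in the kidney and coagulation paragraphs has its row.

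**Renal safety is still monitored.** A reader might infer that the kidney signal goes unmonitored, or that monitoring comes down to creatinine and dipstick protein. The documents do not support that. Sodium, potassium and the full urine stix panel (including red cells, white cells, glucose and pH) are also in sets A and B, and sediment examination follows certain abnormal stix results. Exclusion criteria 24 and 25 keep out subjects with relevant kidney or urinary tract disease or an estimated GFR below 80 mL/min.

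**Urea could still be measured.** A reader might infer that there will be no urea values at all. What the documents show is that none is scheduled. Section 6.2.3 provides for follow-up of clinically relevant abnormal values with appropriate tests, and SAP 7.8.2 has a rule for unscheduled results.

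**Little depends on urea.** It enters no eligibility criterion, discontinuation or stopping rule, AESI definition or visible endpoint. The animal changes in creatinine and urea are reported for the 2-week trials only, at high exposures, and no direction is given for urea. This limits the weight of the point but leaves the contradiction in place.

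**The error may be in the text.** Nothing in the documents shows whether the narrative or the table is wrong. That stands, and the fix allows for either.

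**Conclusion.** The point holds as a mismatch between a stated safety commitment and the schedule meant to deliver it. One of four promised renal items has no row in Table 5.2.3: 1. No urea value is scheduled in any part of the trial, on any of the 520 planned occasions when creatinine is measured. Renal monitoring is incomplete against Section 1.4.2, not absent.

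The practical loss is one descriptive laboratory parameter for a named target organ, together with a benefit-risk statement that is inaccurate as written. No decision rule or endpoint is affected. The finding assumes that the table as read from PDF is complete, and the count assumes that the flow chart entries were read correctly. Both can be settled by looking at the original pages.

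**What to change.** Reconcile Section 1.4.2 with Table 5.2.3: 1.

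- **Preferred:** add urea (BUN) to the Substrates rows of Table 5.2.3: 1 in sets A and B, so that it is measured whenever creatinine is. SAP 7.8.2 would then summarise it without rewording, because that section names no parameters.
- **Alternative:** if the sponsor judges urea unnecessary, remove it from the commitment in Section 1.4.2 and state why creatinine, estimated GFR, electrolytes and urinalysis suffice.

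The preferred option costs one analyte on 6 occasions per SRD subject and 8 per MD or DDI subject. It could presumably run on the chemistry sample already drawn; this is an assumption, since the protocol gives no volume for that sample. Section 5.2.3 also requires a reference range in the investigator site file. Either option needs a protocol amendment, and Section 8.1 requires changes introduced by amendment to be approved by the ethics body and the competent authority before they are implemented. A new row would not help subjects who have already completed the trial; for them, the report should say that urea was not a scheduled measurement.

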- Clinical laboratory tests in the current and preceding dose groups up to at least 7 d post dosing
- Review of criteria for stopping subject treatment as per Section [3.3.4.1](#)

The decision to escalate the dose will be made jointly by the Principal Investigator, or an authorised deputy, Sub Investigator, CTL and TMM after in-depth analysis of all available safety data, especially serious adverse event (SAE)s, AEs, and out-of-range laboratory results that are considered clinically significant by the investigator. Dose escalation will only be permitted if no safety concerns exist neither in the opinion of the Principal Investigator (or an authorised deputy, Sub Investigator), CTL and TMM.

Safety Reviews can be conducted face-to-face or by video/telephone conference. The CTL is responsible for the organisation and minutes of the reviews. Minutes will be signed off by the Principal Investigator (or an authorised deputy, Sub Investigator), CTL and TMM, and will be filed in the investigator site file (ISF) and TMF.

Additional subjects may be entered to allow additional testing on the basis of experience gained during the trial conduct (e.g. preliminary PK data), provided the planned and approved highest dose will not be exceeded and none of the stopping criteria apply. Thus, the actual number of subjects entered may exceed 50, but will not exceed 62 subjects. CTP will be amended if additional subject entry has decided.

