## **7.8.2      Laboratory data**

The analyses of laboratory data will be descriptive in nature and will be based on BI standards "Display and Analysis of Laboratory Data" ([9](#)).

Analyses will be based on normalised values, which means transforming to a standard unit and a standard reference range. The original values will be analysed if the transformation into standard unit is not possible for a parameter.

Descriptive statistics of laboratory values over time and for the difference from baseline (see [Section 6.7](#)) will be provided. Frequency tables of changes between baseline and last value on treatment with respect to the reference range will be presented.

Unscheduled measurements of laboratory data will be assumed to be repeat measurements of the most recent scheduled measurement (e.g. for follow-up or confirmation of a particular value). Therefore, unscheduled measurements will be assigned to the planned time point of the previous scheduled measurement. Descriptive statistics will be calculated by planned time point based on the worst value of the subject at that planned time point (or assigned to that planned time point).

Possibly clinically significant abnormal laboratory values are only those identified either in the Investigator's comments or at the Report Planning Meeting at the latest. It is the Investigator's responsibility to decide whether a lab value is clinically significant abnormal or not. Standard or project-specific rules for flagging clinically significant values in an automated manner will not be applied in this study.

Clinically relevant findings in laboratory data will be reported as baseline conditions (prior to first administration of study treatment) or as AEs (after first administration of study treatment) if judged clinically relevant by the investigator, and will be analysed as such.

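### Prothrombin time and aPTT are named as coagulation mitigation but are scheduled only at screening and end of trial, so completers have no scheduled value while BI 1323495 is expected to act

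*Protocol*

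**What the plan says.** Protocol Section 1.4.2 lists the coagulation pathway among the systems affected in animals. On platelets it reports: "A reduction in platelet counts was associated with BI 1323495 exposure in both rodent and non-rodent species". On clotting time it adds: "This was accompanied at very high exposures by minor increases in prothrombin time in male rats". It describes no aPTT change and states that no bleeding occurred.

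The mitigation paragraph has three parts:
- laboratory tests: "Platelet count, prothrombin time and activated partial thromboplastin time (aPTT) will be measured as part of the standard safety laboratory assessments", with a pointer to Section 5.2.3;
- surveillance for bleeding signs and bleeding-related adverse events;
- a ban on drugs that inhibit platelet aggregation or coagulation.

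In Table 5.2.3: 1 the row "Activated Partial Thromboplastin Time" and the rows for PT and INR are marked in set A and dashed in sets B, C and D. The footnote defines set A: "A: parameters to be determined at Visit 1 and EOT". Fibrinogen is in sets A and B; platelet count is in sets A, B and D.

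Two other places use these data. SAP 7.8.2 promises: "Frequency tables of changes between baseline and last value on treatment with respect to the reference range will be presented". The minimum data set for dose escalation in Protocol Section 3.1 includes: "Clinical laboratory tests in the current and preceding dose groups up to at least 7 d post dosing".

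**The concern.** A test offered as mitigation for a drug effect should be able to show that effect if it occurs. If a PT or aPTT prolongation appears during exposure and resolves as the drug clears, a sample before dosing and another after the residual effect period will both look normal. The trial would then hold unremarkable PT and aPTT results that say little about the dosing period, and a reader of the report could take them as evidence of no effect.

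The arrangement also sits oddly beside the rest of Section 1.4.2. ALT, AST, bilirubin and creatinine, which cover the liver and kidney findings, are all in set B and so are measured after dosing. Set B also carries fibrinogen, whose increase Section 1.4.2 regards as toxicologically unimportant, but not the two clotting times that the same section names.

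**Working it through.** No sample size, power or error rate is involved. The check sets the laboratory sets against the Flow Charts and compares EOT with the end of the residual effect period (REP).

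**Inputs**
- Set contents: Table 5.2.3: 1, as above.
- REP: about 7 days (168 h) for BI 1323495; 9 days (216 h) after the last itraconazole dose on Day 7 (Protocol 1.2.3).
- Dosing days: SRD Day 1; MD last dose Day 11 (240 h); DDI Day 1 of each period.
- EOT: SRD Day 9 to 15; MD Day 19 to 21; DDI Day 16 to 23 of Period 2, with no set A draw between the periods (Flow Charts).

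**Step 1. Scheduled draws from the BI 1323495 dose to the end of the window.** The window ends at the BI 1323495 REP, or at the itraconazole REP in DDI Period 2.

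| Part | Draws | PT, aPTT, INR | Platelets | Fibrinogen |
|---|---|---|---|---|
| SRD (4, 24, 168 h) | 3 | 0 | 3 | 3 |
| MD (2 h to 408 h) | 13 | 0 | 13 | 5 |
| DDI Period 1 (24, 71 h) | 2 | 0 | 2 | 2 |
| DDI Period 2 (23, 71, 119, 167 h) | 4 | 0 | 2 | 2 |
| Total | 22 | 0 | 20 | 12 |

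**Step 2. EOT minus last BI 1323495 dose, in days**
- SRD: 9 − 1 = 8 to 15 − 1 = 14.
- MD: 19 − 11 = 8 to 21 − 11 = 10.
- DDI: 16 − 1 = 15 to 23 − 1 = 22. With at least 11 days between the two BI 1323495 doses, the first scheduled value after the Period 1 dose comes at least 11 + 15 = 26 days later.

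**Step 3. EOT against the end of the REP, in hours, with dosing at 09:00**
- SRD: the REP ends at 168 h. EOT at 09:00 is 192 to 336 h; even midnight at the start of Day 9 is 183 h.
- MD: the REP ends at 240 + 168 = 408 h. EOT at 09:00 is 432 to 480 h; midnight at the start of Day 19 is 423 h.
- DDI: the BI 1323495 REP ends at 168 h. The itraconazole REP ends at 143 + 216 = 359 h (Day 16, 08:00). EOT at 09:00 is 360 to 528 h, so a Day 16 visit lies at the edge of the itraconazole window.

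**Step 4. Consequence for the analysis.** SAP Table 6.1: 1 ends the SRD and MD on-treatment phase 7 × 24 h after the last dose. That table is written for adverse events, but Protocol 7.3.4 applies the same REP rule to laboratory measurements. On that rule EOT values in SRD and MD belong to follow-up, and the shift table has no scheduled PT, aPTT or INR value for completers. The DDI part is left out of this statement because of the Day 16 edge.

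**Step 5. Baseline.** SAP 6.7 takes the last measurement before BI 1323495 in each period. For these tests the only scheduled pre-dose value is from screening, Day −28 to −8, and it would serve DDI Period 2 as well.

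**The case against.** The strongest reply is that Section 1.4.2 does not rest on PT and aPTT. Platelet reduction is the finding reported in both rodent and non-rodent species, and platelets are followed closely after dosing. Bleeding surveillance and the drug restrictions also apply. A reader might infer that coagulation goes unmonitored on treatment; the documents do not support that. The gap is confined to PT, aPTT and INR.

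The signal is also modest: a minor PT rise, in male rats, at very high exposures. The lower mean exposures at the no-observed-adverse-effect levels in the 4-week studies were 33,000 nM for Cmax and 179,000 nM·h for AUC0-24. The highest MD predictions are 496 nM and 6160 nM·h, giving ratios of 33,000/496 ≈ 66 and 179,000/6160 ≈ 29. These are not margins for PT, because the documents do not give the exposure at which PT rose. Still, nothing in them points to PT prolongation at trial exposures, and it would be wrong to speak of a human signal.

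Three further points stand:
- Section 1.4.2 states no timing for PT and aPTT, so there is no literal contradiction with Section 5.2.3. No endpoint or listed stopping criterion uses either test.
- A subject who stops early should have the full EOT examination at that time if possible (Protocol 3.3.4), which could give a value inside the REP. Unscheduled tests are also possible.
- Seven days is a minimum for the escalation data, and the decision uses all available safety data. One cannot say that escalation reviews will lack PT and aPTT, only that the required data set can be complete without any post-dose value.

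None of this gives completers a scheduled value during exposure.

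**Conclusion.** The point holds as a gap between a named mitigation and the schedule meant to deliver it. In all three parts, completers have 0 scheduled PT, aPTT or INR values between the first BI 1323495 dose and the end of that drug's REP after the last dose. The shift table to the last on-treatment value has no scheduled entry for them in SRD and MD. SAP 7.8.2 also plans summaries over time and differences from baseline, where EOT values can appear, but those values cannot show an effect that has already reversed.

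It would go too far to say that the trial cannot detect any coagulation effect: platelets, fibrinogen and bleeding events are all observed on treatment. The narrower conclusion is that a reversible PT or aPTT change could pass unseen in completers under the planned schedule.

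This rests on three assumptions: that the approximate 7-day REP is a fair guide (Section 1.2.3 allows for prolonged exposure with itraconazole); that visits follow the Flow Charts; and that the on-treatment period for laboratory data follows Protocol 7.3.4. The point merits correction, but it does not touch the primary or secondary endpoints.

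**What to change.** Reconcile Section 1.4.2 with Table 5.2.3: 1. The documents do not settle which should change, so the choice is the sponsor's.

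- **Add the tests.** The simplest route is to mark aPTT, PT and INR in set B, a change of three cells. On the existing set B times this gives a baseline closer to dosing (Day −1 in SRD, MD and DDI Period 1; Day −3 in DDI Period 2). It also gives 3, 5, 2 and 2 values in the four windows of the working table, the same 12 as fibrinogen now has. The cost is the assays and possibly a little blood. Fibrinogen is already assayed in set B, so a coagulation sample is presumably taken (assumption); any added volume must be checked against the 400 mL limit per subject.
- **Keep the schedule.** Then Section 1.4.2 should describe PT and aPTT as before-and-after checks, with platelets and fibrinogen as the measures followed on treatment. The SAP should note that the on-treatment shift table has no scheduled PT, aPTT or INR value for SRD and MD completers, and the report should not conclude that there was no on-treatment PT or aPTT effect. This costs only text, but leaves the gap in the data.
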